### **3. Inclusion criteria:**

Subjects included in this study will having all of the following criteria:

- Heel pain with calcaneal spur.
- Calcaneal spur in lateral calcaneal x-ray.
- Patient's age ranged from 30 to 65 years.
- Body mass index less than 30 Kg/M.
- Patients with calcaneal spur.
- Patients with intact sensory perception.
- At least 6 weeks from last corticosteroid injection; 4 weeks from the last local anesthetic injection, iontophoresis, ultrasound, and electrotherapy (**Gerdesmeyer et al., 2008**).

### **4. Exclusive criteria:**

Subjects excluded in this study for any of the following cases:

- History of fracture or surgery of the heel or ankle.
- Presence of inflammatory joint disease.
- Marked osteoporotic patient.
- Presence of ankylosing spondylitis Heart pacemaker use.
- Patient on anticoagulant and coagulation disease.
- Skin wound or ulcers.

## **5. Martials:**

The study materials will divided into two different categories:

### **a. Evaluative Equipment:**

1. X-ray Machine: The best method of assessment of skeletal structure of foot by using radiographic techniques, which considered as the gold standard for assessment bone deformity and alignment of foot in weight bearing position. It will used to scan the foot and calcaneus before and after treatment; it consists of operating console of x ray machine, x ray tube, x ray cassette, digital radiography systems and desktop computer with windows operating system to measure the length and width of the calcaneal spur. (**Rajakaruna et al., 2015**).
2. Pressure pain threshold (PPT): A handheld pressure algometry will be used to measure heel tenderness threshold. The threshold is the minimum force required producing the sensation of pain. The PA is a force gauge equipped with a rubber tip and calibrated in kg/cm^2 (Model FDX, Algometer, WAGNER instruments, Greenwich, CT) (**Alotaibi et al., 2015**).
3. Visual analogue scale (VAS): are used to express the severity of illness (usually pain) by patients by making a mark determining a decimal number from 0 to 100 (mm) on line with 'no pain' to the left and sever pain could be to the right. The subjects rated their perception of pain by making a mark on the VAS line. The distance from the left to the mark will measured and the accuracy will adjusted to one decimal place (see appendix III) (**Kamper, 2012**).

4. Foot and Ankle Ability Measure (FAAM): is a self-report measure that assesses physical function of individuals with lower leg, foot, and ankle musculoskeletal disorders. FAAM is assess activity of daily living ADLs (26 items) and sport activity (8 items). (**Irrgang M et al., 2005**). FAAM is a reliable, responsive, and valid measure of physical function for individuals with a broad range of musculoskeletal disorders of the lower leg, foot, and ankle (**see appendix II**) (**Martin et al, 2005**).

**b. Therapeutic Equipment:**

1. Shockwave apparatus: Gymna Shockmaster 500 device will be used in this study. This device is a radial shockwave device, pneumatically generated and composed from (**Fig12**): Device Shockmaster 500, Communicating Wire between applicator and device, Hand piece applicators that is light ergonomically well design hand piece applicator, D-Actor 20 mm applicator and Trolley Shockmaster 500. The device allow variability in the setting with Frequency range 0,5 - 21 Hz and Pressure range 0,3 - 5 bar.
2. Acetic acid gel: 5% concentration acetic acid gel form will be applied to the foot as a coupling media instead of ultrasound gel between the applicator and the body surface (**Pamplona et al., 2017**).
3. Exercise program: designed to adjust foot mechanics by stretch tight structure and strength the weak muscles.
4. Advices: Dietary advices and advices to alter calcaneal spur pain.

**Figure 12:** shockwave apparatus adapted from <https://gymna.com/en/products/shockwave-therapy/gymna-shockmaster-500>

## **6. Methods:**

A verbal explanation about the important of the study procedure, main aim and conceptual approach will explained to every patient. The procedure of this study will divided into two main procedures:

### **A. Measurement methods:**

Before starting the study, a consent form will be taken from each participant in this study as an agreement to be included in the present study. Each participant will examined medically to exclude any abnormal medical problem, which previously mentioned. Measurement will taken pretest assessment and posttest assessment and post one month follow up as follow:

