### ➤ **Statement of the Problems:**

There is a gap in literature on the effect of Shockwave in combination with substance like acetic acid gel on treatment of calcaneal spur patients. So, this study conducted to answer the following question:

- Dose the extracorporeal acetic acid shockwave phonophoresis has any effect on length of calcaneal spur, pain pressure threshold, pain level and physical function in patients with calcaneal spur?
- Dose the extracorporeal shockwave has any effect on length of calcaneal spur, pain pressure threshold, pain level and physical function in patients with calcaneal spur?
- Is there a statically significant difference between extracorporeal shockwave and extracorporeal acetic acid shockwave phonophoresis on length of calcaneal spur, pain pressure threshold, pain level and physical function in patients with calcaneal spur?

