Furthermore, conflicting reports exist in the literature as to whether at all radial extracorporeal Shockwave (RSWT) can generate cavitation, which refers to the rapid formation, expansion, and forceful collapse of vapor bubbles in liquids subject to rapid pressure changes. Cavitation exerts important therapeutic bioeffects; also produce unwanted side effects including hematomas, blood vessel rupture, and permanent injury to organs such as kidneys and lungs. In this respect an early review about ESWT published in 2003, 2006, 2015 concluded that RSWT devices were in fact capable of generating cavitation. In conclusion, FSWT & (RPWT) or (RSWT) produce cavitation activity which is limited to the area of the applicator head in RSWT applicators .**(Contaldo et al., 2012)(Császár et al., 2015).**

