### g. Shockwave and calcaneal spur:

The primary effect is the direct mechanical forces that result in the maximal beneficial pulse energy concentrated at the treatment site. in addition to that, the secondary effect is the indirect mechanical forces by cavitation, which may cause negative effect or damage to the tissues which can help in calcaneal spur destruction (Wang, 2012)(Frairia & Berta, 2011) (Schmitz C et al., 2013)

Xian Li et al., conducted meta-analysis research compared the effectiveness of eight modalities for treating plantar fasciitis (Shockwave therapy), both Intracorporeal pneumatic shock therapy (IPST) and extracorporeal shock therapy (FSWT (3 groups low, medium, high energy flux density), RSWT), Low level LASER therapy, Ultrasound therapy (US), and noninvasive interactive neurostimulation (NIN) ultrasound-guided pulsed radiofrequency (UGPRF) treatment were included. The therapies compared these modalities with each other or with a sham group. Regarding the three follow up effectiveness time points, RSWT provided relatively

more effective and stable pain relief compared with other modalities. Consequently, RSWT is a promising candidate for clinical applications. FSW therapies and US can also be considered treatment candidates. However, H-FSW and UGPRF not recommended (**X. Li et al., 2018**).

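### No harm is recorded or reported by arm, so a benefit of the acid gel could be claimed with no data on skin or bruising effects, and losses due to them would go unexplained

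*Combined protocol and SAP*

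**What the plan says.** **Entry screen.** The exclusion list (Chapter III, section 4) includes "Skin wound or ulcers", anticoagulant use and coagulation disease. Section 6.A (Measurement methods) opens with consent, "Before starting the study, a consent form will be taken from each participant in this study", and the next sentence reads "Each participant will examined medically to exclude any abnormal medical problem, which previously mentioned". No repeat of that examination is described.

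**Assessments.** Section 6.A continues: "Measurement will taken pretest assessment and posttest assessment and post one month follow up as follow". The four subsections that follow cover spur length and width on X-ray, pressure pain threshold (PPT), VAS and FAAM.

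**Treatment.** Groups A and B each have six shockwave sessions, with intensity set to the most the patient can tolerate (section 2, Subjects; section 6.B). In Group A, "5% concentration acetic acid gel form will be applied to the foot as a coupling media instead of ultrasound gel". Group B uses ordinary ultrasound coupling gel.

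**Harms named in the review of literature.** On cavitation, the subsection comparing focused and radial shockwave says it can "also produce unwanted side effects including hematomas, blood vessel rupture, and permanent injury to organs such as kidneys and lungs", and concludes that radial devices also cavitate, near the applicator head. The subsection on shockwave and calcaneal spur describes indirect forces by cavitation, "which may cause negative effect or damage to the tissues which can help in calcaneal spur destruction".

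**Novelty.** The Statement of the Problems says: "There is a gap in literature on the effect of Shockwave in combination with substance like acetic acid gel".

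**Data and analysis.** The Data collection section mentions a data collection sheet without listing its fields. The Statistical Analysis section covers group comparisons, normality checks and multiplicity. It lists no safety summary.

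**The concern.** Harm data that are not collected during a trial cannot be recovered at the analysis. The A-versus-B contrast asks whether the acid gel adds anything to shockwave, and a reader will want both sides of that answer. As described, the trial can produce estimates for pain, tenderness, function and spur size, but none for skin reaction, bruising or hematoma. These are the local effects most closely tied to the gel and to the cavitation that the background discusses.

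The second issue is bias. No reason for a missed session or withdrawal is described as being recorded. If some patients leave because of a local reaction, they would appear only as unexplained losses. If such losses were more common in one arm, the efficacy comparison would be distorted and the analyst could not see why. The documents do not show that this will happen; the plan simply has no means of detecting it.

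A related silence concerns the exclusion criteria. They are described as an entry screen, and nothing says whether they also apply across the six sessions or who decides if one is newly met.

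**Working it through.** **1. What each described measure could show.**

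| Measure | When | Could reveal | Does not record |
|---|---|---|---|
| X-ray | before, after | spur size; incidentally a fracture | skin or vessel injury |
| PPT | pretest, posttest, one month | greater tenderness | its cause; a bruise or wound |
| VAS | same | worse pain | its cause |
| FAAM | same | worse function | its cause |

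Three assessment times are scheduled and none falls between the six sessions. None of the four instruments is a harm measure, and no safety analysis is listed. The intensity rule in section 6.B responds to tolerated pain during treatment. It is not a record of harm.

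**2. Exposure.** Inputs: 20 patients per group and 6 sessions (section 2, Subjects).
- Per shockwave arm: 20 × 6 = 120 sessions.
- Groups A and B together: 2 × 120 = 240 sessions.

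**3. What recording would yield.** The plan gives no harm rate and no sample-size calculation, so there is no figure to reproduce. True per-patient risks p of 1%, 5% and 10% are my assumptions.

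Chance of at least one case: 1 − (1 − p)^n.
- n = 20: 1 − 0.99^20 = 18.2%; 1 − 0.95^20 = 64.2%; 1 − 0.90^20 = 87.8%.
- n = 40: 1 − 0.99^40 = 33.1%; 1 − 0.95^40 = 87.1%; 1 − 0.90^40 = 98.5%.

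Exact one-sided 95% upper bound after zero cases: 1 − 0.05^(1/n).
- n = 20: 13.9%.
- n = 40: 7.2%.

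**4. Sensitivity to the group-size conflict.** Section 2 states forty patients in two equal groups but lists three groups of 20 (3 × 20 = 60). The figures above use 20 per group. If forty were spread over three arms, about 13 each, the zero-case bound would be 1 − 0.05^(1/13) = 20.6%.

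**5. Why tabulation rather than a test.** Assume true risks of 20% in A and 5% in B, 20 per arm, two-sided α = 0.05, normal approximation. The pooled risk is 0.125.
- Null standard error: √(0.125 × 0.875 × 2/20) = 0.1046.
- Alternative standard error: √((0.20 × 0.80 + 0.05 × 0.95)/20) = 0.1019.
- Power: Φ((0.15 − 1.96 × 0.1046)/0.1019) = Φ(−0.54) ≈ 29%.

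A formal comparison of harms would therefore be uninformative even for a large difference. A descriptive table is what this sample size supports.

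**The case against.** **The trial is not wholly blind to harm.** VAS, PPT and FAAM can show worsening, the investigator palpates the heel for PPT, and the post-treatment film could show a fracture. This stands, and it would be too strong to say that the trial can learn nothing about harm. None of these measures records a skin, bruising or vessel effect or attributes a change to one.

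**A reader might infer that a patient who develops a heel wound or starts an anticoagulant mid-course is still treated.** The documents do not say so. They are silent, and the exclusion list carries no explicit limit to entry. The examination sentence also has no date of its own. Reading it as a pre-study check is natural because it directly follows the consent sentence, but that remains a reading.

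**The background can be over-read.** The hematoma and organ-injury sentence is about cavitation in general and does not attribute those harms to radial devices specifically. Kidney and lung injury has no stated link to heel treatment. The Statement of the Problems reports a literature gap, which is less than saying the combination has never been studied. The protocol also cites a review that found both shockwave modalities safe, and says potential risks are explained to participants. Those points stand, but the cited review is about shockwave therapies, not shockwave with acid gel, and explaining a risk is not recording it.

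**Relevant wording may exist elsewhere.** The consent form was removed before review and the data sheet is not reproduced. Either may cover withdrawals or adverse events. The point is therefore limited to what the available text describes.

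**Conclusion.** The concern holds in this form: the available text describes no collection and no by-arm reporting of harms, although the background names local tissue risks and the gel is the planned A-versus-B difference. A finding in favour of Group A could be published with no record of skin or bruising effects over 120 sessions, and losses caused by such effects would be unexplained.

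The gain from fixing this is real but bounded. With 20 per arm, recording would probably show a harm with a true risk of 10% (88% chance of at least one case), and would usually miss one with a risk of 1% (18%). Zero cases would still be compatible with a risk of up to 13.9% in one arm, or 7.2% over 40 shockwave patients. These figures rest on assumed risks and on 20 patients per group.

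On the exclusion criteria, the supportable conclusion is that the plan does not say whether they apply during treatment. It does not follow that newly ineligible patients would continue. The matter should be settled before enrolment, because harm information not gathered at the sessions is lost.

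**What to change.** 1. **Record at existing shockwave sessions (Groups A and B).** Add fields to the data collection sheet for skin reaction, bruise or hematoma, pain outlasting the session, and the reason for any missed session.
2. **Ask one identical harm question in every arm** at posttest and at one month. Group C has no shockwave sessions, so this question is the only harm item comparable across all three arms.
3. **Report by arm.** In Statistical Analysis, state that harms and reasons for missed sessions will be tabulated by arm with the efficacy results, as counts of patients with denominators, and that no safety statement will go beyond those data. Reconcile the forty-patient and three-groups-of-20 statements, since they set the denominators.
4. **Clarify the exclusion criteria.** The sponsor should state whether section 4 applies during the six sessions and who decides if a criterion is newly met. The content of that clinical rule is for the sponsor, and none is proposed here.

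The cost is a few extra lines on an existing sheet and a little recording time at visits already planned. No extra visit or procedure is needed. The limitation is that the result informs on common local harms only. If the consent form or data sheet already contains such items, citing them in the protocol and adding the by-arm table may be enough.

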#### **1. X-ray:**

Lateral calcaneal x-ray helps to evaluate bony conditions of the foot for example, Calcaneal spur, calcaneal stress fractures may be visualized on lateral calcaneal and that help in excluding any condition not suitable with

this research. Each patient should do at least two x-rays ,one before and another after, computer aided linear measurements will recorded for spur length and width in (mm) from tip to base as defined by a line determining the calcaneal border as described by many authors (**Fig. 13**) (**Kuyucu et al.,2015**)(**Büyükturan, 2017**) (**Gladman et al., 2014**)

*Figure 13 : X-ray machine*

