Moreover, Moroney et al., concluded that the calcaneal spur and planter facilities are separated phenomena and planter heel pain patient can be complain from spur, fasciitis or both. In addition, Li and Muehleman have documented that the trabeculae within these calcaneal spurs are not oriented in the direction of soft-tissue traction but rather in a vertical orientation (**Moroney et al., 2014**).

Li & Muehleman et al., the calcaneal Spur may be closely associated with any intrinsic muscle on the first layer of the foot which consists of the abductor hallucis (AH), flexor digitorum brevis (FDB) and abductor digiti minimi (ADM); The second layer consists of quadratus plantae and it attaches deep to the calcaneal Spur. Tanz (1963) was one of the earliest authors to show that calcaneal Spur can arise from muscle rather than from the planter fascia itself. The FDB attaches to the medial process of the calcaneal tuberosity or the apex of the calcaneal Spur if present, anterior and superior to the attachment of the planter fascia (Forman & Green, 1990). The FDB inserts into the periosteum of the calcaneal Spur along with the planter fascia in (22%) of cases, most commonly at the spurs distal tip and

inferior aspects (14%), but also at the superior aspect 8% (**Li & Muehleman., 2007**)

The calcaneal Spur is oriented along the axis of the planter fascia and FDB approximately half of the time Abreu et al., The ADM also attaches directly to the calcaneal Spur, although not as extensively as the FDB does; the calcaneal Spur is aligned with the ADM 20–50% of the time (Smith et al. 2007). The AH arises just medial to the FDB origin and has been hypothesized to contribute to calcaneal Spur formation (Forman & Green, 1990). calcaneal Spur have also been shown to arise from around the calcaneal insertion point of the long plantar ligament (**Smith et al., 2007**) (**Abreu et al., 2003**) (**Kirkpatrick et al., 2017**)

Factors which may be important in determining whether a given calcaneal spur will cause an individual heel pain include the size of the spur, whether there is compression of the inferior calcaneal nerve, spur fractures, concurrent inflammation, fat pad abnormalities or degeneration, and the individual's occupational environment (**Kirkpatrick et al., 2017**).

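### Post-treatment films are read only for spur size, so a fracture or separated spur fragment visible on them has no place in the trial data

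*Combined protocol and SAP*

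**What the plan says.** All references are to the combined protocol and SAP.

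- **Chapter III, 5.a Evaluative Equipment:** the foot and calcaneus are scanned before and after treatment, and the stated purpose is "to measure the length and width of the calcaneal spur".
- **Chapter III, 6.A.1 X-ray, number of films:** "Each patient should do at least two x-rays ,one before and another after".
- **Same section, what is recorded:** "computer aided linear measurements will recorded for spur length and width in (mm) from tip to base", with the base "as defined by a line determining the calcaneal border as described by many authors". Nothing is said about how to measure when part of the spur has separated.
- **Same section, what else the film can show:** "calcaneal stress fractures may be visualized on lateral calcaneal and that help in excluding any condition not suitable with" the research. Visible fracture is mentioned only in connection with exclusion.
- **Chapter II, 2.g Shockwave and calcaneal spur:** the indirect effect of shockwave, through cavitation, is one "which may cause negative effect or damage to the tissues which can help in calcaneal spur destruction".
- **Chapter II, 1.d Calcaneal spur and planter fasciitis:** the factors that may decide whether a given spur hurts include "whether there is compression of the inferior calcaneal nerve, spur fractures, concurrent inflammation".
- **Chapter III, Data collection and Statistical Analysis:** a data collection sheet is mentioned but its items are not listed. Neither section provides for adverse events, and nor do the measurement sections.

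**The concern.** The plan obtains a film that could show bone injury, after a treatment that its own review links to tissue damage and spur destruction, and takes only two linear measurements from it. Two things follow.

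**Safety.** A calcaneal fracture, a separated spur fragment or another new bone lesion on the later film would have no field to go into and no route into the report. The trial could not report such a case. Nor could it credibly report that none occurred, because nobody was asked to look.

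**Interpretation.** Spur length is an outcome in all three null hypotheses. If a tip separates and the reader measures the attached remnant to the calcaneal border, the recorded length falls although no calcium has dissolved. The rationale for the acid is chemical: it is meant to turn insoluble calcium carbonate into a soluble salt. A length figure alone cannot separate that process from breakage within a group.

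**Working it through.** The plan gives no figure to reproduce: no fracture rate, no breakage rate and no expected change in spur length. The check is therefore first a comparison of sections, then an illustration with assumed inputs.

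**Step 1. What the film can show against what is recorded**

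| Question | Where | Answer |
|---|---|---|
| Can the film show fracture? | 6.A.1 X-ray | Yes, mentioned for exclusion |
| Is a film taken after treatment? | 5.a and 6.A.1 | Yes, in every patient |
| What is recorded from it? | 5.a and 6.A.1 | Spur length and width |
| Is there a rule for a fragment? | 6.A.1 | None |
| Are adverse events recorded elsewhere? | Chapter III | No provision found |

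**Step 2. Which comparisons a broken tip could affect**

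Under Therapeutic methods, Groups A and B are both to have shockwave once a week for six weeks at the highest level the patient tolerates. They differ in the coupling gel: 5% acetic acid in A, ultrasound gel in B. Group C has exercise and no shockwave.

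- *A versus B:* breakage caused by shockwave is expected equally in both groups under randomisation, so its expected contribution to the difference is zero.
- *A versus C, B versus C:* any such breakage can occur only in the shockwave group, so it enters the difference in full.
- *Change within A or within B:* it enters in full.

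**Step 3. Illustrative shift of one group's mean**

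Inputs: 20 per group (Subjects section). The number of breaks k and the length lost L are assumed. Shift = k × L / 20.

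| Breaks in 20 | L = 1 mm | L = 2 mm | L = 3 mm |
|---|---|---|---|
| 0 | 0 | 0 | 0 |
| 1 | 0.05 mm | 0.10 mm | 0.15 mm |
| 2 | 0.10 mm | 0.20 mm | 0.30 mm |
| 3 | 0.15 mm | 0.30 mm | 0.45 mm |

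These are shifts in a single group. For A versus B only the difference in k matters. An imbalance of one break, by chance, would move that contrast by 0.05 to 0.15 mm in either direction.

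**Step 4. Chance that the trial would have a case to record**

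Inputs: 40 patients exposed in A and B together. The per-patient risk p of a visible bone injury is assumed. P(at least one) = 1 − (1 − p)^40.

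| Assumed p | P(at least one in 40) |
|---|---|
| 1% | 33% |
| 2% | 55% |
| 5% | 87% |
| 10% | 99% |

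If the films were read for bone injury and none were found in 40, the one-sided 95% upper bound on the risk would be 1 − 0.05^(1/40) = 7.2%. The plan as written cannot support even that statement.

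**The case against.** The strongest reply is that the contrast isolating the acid is A versus B, and there the shockwave rule is the same. This stands. A reader might infer that breakage makes the effect of acetic acid on spur length uninterpretable, and the documents do not support that. If the acid itself made breakage more frequent, that too would be an effect of the acid on length, and the aims ask about length without restricting it to dissolution. What remains for A versus B is chance imbalance.

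Second, a reader might infer that the plan scores a broken spur as a success. It does not. Spur length is a continuous outcome, no success category exists, and no section formally says that a shorter spur is an improvement. With no fragment rule, a reader of the film might also measure to the original tip of a fragment still in line. The supportable statement is that a separated tip *can* be counted as a reduction.

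Third, a reader might infer that the documents predict fracture of the calcaneus. They do not. Section 2.g speaks of tissue damage and spur destruction and presents this as part of how treatment works. Section 1.d lists spur fracture as a factor in pain, without reference to shockwave. The trial device is radial (5.b Therapeutic Equipment), and section 2.e says that cavitation from radial applicators is confined to the area of the applicator head. The unwanted effects of cavitation named there do not include bone injury. The risk may be low.

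Fourth, the X-ray section does not expressly confine bony evaluation to baseline, and the data collection sheet is not reproduced. Both are true, but exclusion is the only use of fracture findings that is mentioned, and no text asks for them afterwards.

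None of these replies supplies a place for the finding. They narrow the interpretation argument and leave the recording gap.

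**Conclusion.** The point holds as a gap in safety recording, with a smaller consequence for spur length. As written, bone injury visible on the post-treatment film would not enter the trial data, and a separated tip can be measured as a shorter spur. The second effect concerns within-group change and the comparisons with Group C. A versus B is largely protected.

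The size is unknown, because the documents give no rate of fracture or breakage. The shifts of 0.05 to 0.45 mm and the probabilities of 33% to 99% rest wholly on assumed inputs, and zero breaks is also possible. They show what the plan would be unable to detect, and they are not estimates of bias. The section 1.d definition of a spur as a projection of more than 1 or 2 mm is a threshold for calling something a spur. It should not be used to judge whether a shift in a group mean matters.

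This is a cheap improvement, worth making for safety reporting. It does not invalidate the planned comparison of the two shockwave groups.

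**What to change.** In 6.A.1 X-ray:

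1. When the post-treatment film is measured, compare it with the baseline film and record yes or no for calcaneal fracture, separated spur fragment and other new bone lesion. The reader should preferably be unaware of group.
2. Report the three findings by arm as safety results, including zeros, and notify the responsible investigator of any positive finding.
3. State in advance one rule for measuring spur length when a fragment is present, and apply it in all groups.
4. Keep all randomised patients in the spur-length comparison and report the number with a fragment in each arm beside it. Do not repeat the comparison without those patients. Breakage occurs after randomisation and may be caused by treatment, so excluding on it would break the randomised comparison.

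Cost: no extra film and no extra radiation, three added fields, and slightly more reading and reporting. The documents do not say who reads the films. That person must be able to recognise these lesions, which is more than linear measurement requires, so a suitably qualified reader may have to be named.
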